## **6. DATA COLLECTION, MONITORING, AND REPORTING**

### **6.1. Data Collection**

Data will be prospectively collected and entered into the database at least once every two weeks. The NCI C3D database will be used for this study. The responsible investigator is [name].

Complete records must be maintained on each patient. These will consist of the hospital chart with any supplementary information obtained from outside laboratories, radiology reports, or physician's records. These records will serve as the primary source material that forms the basis for the research record. All relevant data will also be entered into the NCI C3D database from which formal analyses are done. The primary source documentation will assure the following: on study information, including patient eligibility data and patient history; and off-study summary sheets, including a final assessment by the treating physician. All data will be kept secure. Personal identifiers will not be used when collecting and storing data. An enrollment log will be maintained in the regulatory binder/file which is the only location of personal identifiers with unique subject identification number.

Laboratory data collected from outside of the NIH Clinical Center will be entered into C3D manually. Training will be provided to the participating institutions by the NIH.

Data will be submitted to the CTEP/CDUS every three months via the NCI C3D database.

### **6.2 Data Reporting**

#### **6.2.1 Method**

This study will be monitored by the Clinical Data Update System (CDUS) version 3.0. Cumulative CDUS data will be submitted quarterly to CTEP by electronic means. Reports are due January 31, April 30, July 31, and October 31. Instructions for submitting data using the CDUS can be found on the CTEP Web site ([http://ctep.cancer.gov/protocolDevelopment/electronic\\_applications/cdus.htm](http://ctep.cancer.gov/protocolDevelopment/electronic_applications/cdus.htm)).

**Note:** All adverse events that have occurred on the study, including those reported through AdEERS, must be reported via CDUS.

#### **6.2.2 Responsibility for Submissions**

Participating institutions are responsible for submitting CDUS data and/or data forms to the Coordinating Center quarterly by January 10, April 10, July 10, October 10 to allow time for Coordinating Center compilation, Principal Investigator review, and timely submission to CTEP (see Section 11.1.).

The Coordinating Center is responsible for compiling and submitting CDUS data to CTEP for all participants and for providing the data to the Principal Investigator for review.

### **6.3 Data and Safety Monitoring Plan**

The principal investigator will review all serious adverse events and will monitor the data and toxicities to identify trends monthly. The principal investigator will be responsible for revising the protocol as needed to maintain safety. The NCI IRB will review submitted adverse events monthly to also evaluate trends and will require a follow up plan from the principal investigator whenever a trend is identified.

A CCR Safety Monitoring Committee will monitor toxicity trends on this study on at least an annual basis and report any trends to the NCI IRB and Principal Investigator.

The principal investigator will review accrual to both the screening and enrollment phases of the trial every 12 months. If fewer participants than anticipated are enrolling in the treatment phase, the reasons for lack of enrolment will be reviewed and discussed with the Sponsor.

## **7. ADVERSE EVENTS: LIST AND REPORTING REQUIREMENTS**

Adverse event (AE) monitoring and reporting is a routine part of every clinical trial. The following list of AEs (Section 7.1) and the characteristics of an observed AE (Section 7.2) will determine whether the event requires expedited (via AdEERS) reporting **in addition to** routine reporting.

**7.1 Comprehensive Adverse Events and Potential Risks List (CAEPR)**  
**Comprehensive Adverse Events and Potential Risks list (CAEPR)**  
**for**  
**Lapatinib (GW572016, NSC 727989)**

The Comprehensive Adverse Event and Potential Risks list (CAEPR) provides a single list of reported and/or potential adverse events (AE) associated with an agent using a uniform presentation of events by body system. In addition to the comprehensive list, a subset, the Agent Specific Adverse Event List (ASAEL), appears in a separate column and is identified with **bold** and *italicized* text. This subset of AEs (ASAEL) contains events that are considered 'expected' for expedited reporting purposes only. Refer to the 'CTEP, NCI Guidelines: Adverse Event Reporting Requirements' [http://ctep.info.nih.gov/protocolDevelopment/default.htm#adverse\\_events\\_aadeers](http://ctep.info.nih.gov/protocolDevelopment/default.htm#adverse_events_aadeers) for further clarification. Frequency is provided based on 1890 patients. Below is the CAEPR for Lapatinib (GW572016).

Version 2.4, January 6, 2010

Adverse Events with Possible Relationship to Lapatinib (GW572016) (CTCAE 4.0 Term) [n= 1890]			EXPECTED AEs FOR ADEERS REPORTING  Agent Specific Adverse Event List (ASAEL)
Likely (>20%)	Less Likely (<=20%)	Rare but Serious (<3%)	Expected
CARDIAC DISORDERS		Left ventricular systolic dysfunction	Left ventricular systolic dysfunction
GASTROINTESTINAL DISORDERS			
	Abdominal distension		Abdominal distension
	Abdominal pain		Abdominal pain
Diarrhea			Diarrhea
	Dyspepsia		Dyspepsia
	Flatulence		Flatulence
	Gastrointestinal disorders – Other (Mucositis/stomatitis – Select)		Gastrointestinal disorders – Other (Mucositis/stomatitis – Select)
Nausea			Nausea
	Vomiting		Vomiting
GENERAL DISORDERS AND ADMINISTRATION SITE CONDITIONS			
	Fatigue		Fatigue
	Flu like symptoms		Flu like symptoms
HEPATOBILIARY DISORDERS		Hepatic failure	Hepatic failure
IMMUNE SYSTEM DISORDERS		Allergic reaction	
INVESTIGATIONS			
	Alanine aminotransferase increased		Alanine aminotransferase increased
	Aspartate aminotransferase increased		Aspartate aminotransferase increased
	Blood bilirubin increased		Blood bilirubin increased
		Electrocardiogram QT	Electrocardiogram QT

		corrected interval prolonged	corrected interval prolonged
METABOLISM AND NUTRITION DISORDERS			
	Anorexia		Anorexia
	Dehydration		Dehydration
NERVOUS SYSTEM DISORDERS			
	Dysgeusia		Dysgeusia
	Headache		Headache
RESPIRATORY, THORACIC AND MEDIASTINAL DISORDERS			
		Pneumonitis	
SKIN AND SUBCUTANEOUS TISSUE DISORDERS			
	Nail loss		
	Pruritus		Pruritus
	Rash acneiform		Rash acneiform
Rash maculo-papular			Rash maculo-papular
VASCULAR DISORDERS			
	Flushing		Flushing

This table will be updated as the toxicity profile of the agent is revised. Updates will be distributed to all Principal Investigators at the time of revision. The current version can be obtained by contacting [[contact]](mailto:[contact]). Your name, the name of the investigator, the protocol and the agent should be included in the e-mail.

**Also reported on Lapatinib (GW572016) trials but with the relationship to Lapatinib (GW572016) still undetermined:**

**BLOOD AND LYMPHATIC SYSTEM DISORDERS** - Anemia; Febrile neutropenia

**CARDIAC DISORDERS** - Atrial fibrillation; Restrictive cardiomyopathy

**EYE DISORDERS** - Blurred vision

**GASTROINTESTINAL DISORDERS** - Constipation; Dysphagia; Gastritis; Gastrointestinal disorders – Other (Hemorrhage, GI – Select); Gastrointestinal disorders – Other (Obstruction, GI – Select)

**GENERAL DISORDERS AND ADMINISTRATION SITE CONDITIONS** - Edema limbs; Fever; Pain

**INFECTIONS AND INFESTATIONS** – Infections and infestations – Other (Infection – Select)

**INVESTIGATIONS** - Alkaline phosphatase increased; Creatinine increased; Lymphocyte count decreased; Neutrophil count decreased; Platelet count decreased; Weight loss; White blood cell decreased

**METABOLISM AND NUTRITION DISORDERS** - Hyperglycemia; Hypoalbuminemia; Hypoglycemia; Hypokalemia; Hyponatremia; Hypophosphatemia

**MUSCULOSKELETAL AND CONNECTIVE TISSUE DISORDERS** - Arthralgia; Back pain; Myalgia

**NERVOUS SYSTEM DISORDERS** - Cerebrospinal fluid leakage; Depressed level of consciousness; Dizziness; Intracranial hemorrhage

**PSYCHIATRIC DISORDERS** - Insomnia

**RENAL AND URINARY DISORDERS** - Acute kidney injury

**RESPIRATORY, THORACIC AND MEDIASTINAL DISORDERS** - Cough; Dyspnea; Epistaxis; Pleural effusion

**SKIN AND SUBCUTANEOUS TISSUE DISORDERS** - Alopecia; Dry skin; Palmar-plantar erythrodysesthesia syndrome; Skin and subcutaneous tissue disorders - Other (seborrheic dermatitis); Urticaria

**VASCULAR DISORDERS** - Hypotension; Thromboembolic event; Vascular disorders - Other (hypovolemia)

**Note:** Lapatinib (GW572016) in combination with other agents could cause an exacerbation of any

adverse event currently known to be caused by the other agent, or the combination may result in events never previously associated with either agent.

## 7.2 Adverse Event Characteristics

- **CTCAE term (AE description) and grade:** The descriptions and grading scales found in the revised NCI Common Terminology Criteria for Adverse Events (CTCAE) version 4.0 will be utilized for AE reporting. All appropriate treatment areas should have access to a copy of the CTCAE version 4.0. A copy of the CTCAE version 4.0 can be downloaded from the CTEP web site [http://ctep.cancer.gov/protocolDevelopment/electronic\\_applications/ctc.htm](http://ctep.cancer.gov/protocolDevelopment/electronic_applications/ctc.htm).
- **“Expectedness”:** AEs can be ‘Unexpected’ or ‘Expected’ (see Section 7.1 above) for expedited reporting purposes only. ‘Expected’ AEs (the ASAEL) are ***bold and italicized*** in the CAEPR (Section 7.1).
- **Attribution** of the AE:
  - Definite – The AE is *clearly related* to the study treatment.
  - Probable – The AE is *likely related* to the study treatment.
  - Possible – The AE *may be related* to the study treatment.
  - Unlikely – The AE is *doubtfully related* to the study treatment.
  - Unrelated – The AE is *clearly NOT related* to the study treatment.

## 7.3 Expedited Adverse Event Reporting

7.3.1 Expedited AE reporting for this study must use AdEERS (Adverse Event Expedited Reporting System), accessed via the CTEP home page (<http://ctep.cancer.gov>). The reporting procedures to be followed are presented in the “CTEP, NCI Guidelines: Adverse Event Reporting Requirements” which can be downloaded from the CTEP home page (<http://ctep.cancer.gov>). These requirements are briefly outlined in the table below (Section 7.3.3).

In the rare event when Internet connectivity is disrupted a 24-hour notification is to be made to NCI by telephone at [contact]. An electronic report **MUST** be submitted immediately upon re-establishment of internet connection. Please note that all paper AdEERS forms have been removed from the CTEP website and will no longer be accepted.

7.3.2 AdEERS is programmed for automatic electronic distribution of reports to the following individuals: Study Coordinator of the Lead Organization, Principal Investigator, and the local treating physician. AdEERS provides a copy feature for other e-mail recipients.

7.3.3 Expedited Reporting Guidelines – AdEERS Reporting Requirements for Adverse Events that occur within 30 Days of the Last Dose of the

Investigational Agent on Phase 2 and 3 Trials

Phase 2 and 3 Trials									
	Grade 1	Grade 2	Grade 2	Grade 3		Grade 3		Grades 4 & 5 	Grades 4 & 5 
	Unexpected and Expected	Unexpected	Expected	Unexpected with Hospitalization	without Hospitalization	Expected with Hospitalization	without Hospitalization	Unexpected	Expected
Unrelated Unlikely	Not Required	Not Required	Not Required	10 Calendar Days	Not Required	10 Calendar Days	Not Required	10 Calendar Days	10 Calendar Days
Possible Probable Definite	Not Required	10 Calendar Days	Not Required	10 Calendar Days	10 Calendar Days	10 Calendar Days	Not Required	24-Hour; 5 Calendar Days	10 Calendar Days

 Adverse events with attribution of possible, probable, or definite that occur greater than 30 days after the last dose of treatment with an agent under a CTEP IND require reporting as follows:  
AdEERS 24-hour notification followed by complete report within 5 calendar days for:

- Grade 4 and Grade 5 unexpected events

AdEERS 10 calendar day report:

- Grade 3 unexpected events with hospitalization or prolongation of hospitalization
- Grade 5 expected events

 Although an AdEERS 24-hour notification is not required for death clearly related to progressive disease, a full report is required as outlined in the table.

December 15, 2004

**Note: All deaths on study require both routine and expedited reporting regardless of causality. Attribution to treatment or other cause must be provided.**

- Expedited AE reporting timelines defined:
  - “24 hours; 5 calendar days” – The investigator must initially report the AE via AdEERS within 24 hours of learning of the event followed by a complete AdEERS report within 5 calendar days of the initial 24-hour report.
  - “10 calendar days” - A complete AdEERS report on the AE must be submitted within 10 calendar days of the investigator learning of the event.
- Any medical event equivalent to CTCAE grade 3, 4, or 5 that precipitates hospitalization (or prolongation of existing hospitalization) must be reported regardless of attribution and designation as expected or unexpected with the exception of any events identified as protocol-specific expedited adverse event reporting exclusions.
- Any event that results in persistent or significant disabilities/incapacities, congenital anomalies, or birth defects must be reported via AdEERS if the event occurs following treatment with an agent under a CTEP IND.

Use the NCI protocol number and the protocol-specific patient ID assigned during trial registration on all reports.

#### **7.3.4 Protocol-Specific Expedited Adverse Event Reporting Exclusions**

For this protocol only, certain AEs/grades are exceptions to the Expedited Reporting Guidelines and do not require expedited reporting (i.e., AdEERS). The following AEs must be reported through the routine reporting mechanism (Section 7.4):

- Grade 2 or greater pain with or without hospitalization
- Events related to vascular access devices with or without hospitalization
- Grade 2 or greater lab abnormalities with or without hospitalization that do not support a reportable adverse event

#### **7.3.5 Additional Protocol-Specific Expedited Reporting Requirements**

- *Cardiac Events*

Cardiac dysfunction will be reported as an SAE and will be defined as any signs or symptoms of deterioration in left ventricular cardiac function that are Grade 3 (NCI CTCAE) or a  $\geq 20\%$  decrease in LVEF relative to baseline which is below the institution's lower limit of normal. See section 5.2.1 for additional information regarding cardiac event reporting.

*Note:* Refer to NCI CTCAE grading of left ventricular cardiac function.

- *Pulmonary Events*

If a patient develops symptoms suggestive of interstitial pneumonitis, adult respiratory distress syndrome (ARDS), or non-cardiogenic pulmonary edema, lapatinib therapy should be interrupted and a thorough evaluation performed. If NCI-CTCAE v4.0 Grade 3 or 4 pneumonitis or pulmonary fibrosis is confirmed (and the relationship to lapatinib cannot be excluded), lapatinib must be permanently discontinued. All incidences of interstitial lung disease/interstitial pneumonitis regardless of grade will be reported as serious adverse events (SAEs).

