## 5. TREATMENT PLAN

### 5.1 Lapatinib Administration

Treatment will be administered on an outpatient basis. Reported adverse events and potential risks are described in Section 7. Appropriate dose modifications lapatinib

are described in Section 5.2 below. No investigational or commercial agents or therapies other than those described below may be administered with the intent to treat the patient's malignancy.

Lapatinib will be administered as an oral dose of 500 mg twice daily (in the morning and evening). All medications are given daily for 28 days, 28 days (4 weeks) equals one cycle. The first course will consist of 28 days (one cycle). All subsequent courses will consist of 2 cycles. Up to 27 cycles may be administered (14 courses, approximately 2 years).

Patients will be instructed to take the medications at the same time each day taken one hour before or after meals. Patients will be advised not to consume grapefruit or grapefruit juice while taking the study medications. The patient will be requested to maintain a medication diary of each dose of medication and any side effects and/or adverse events the patient may experience. The medication diary will be returned to clinic staff at the end of each course.

Prior to discharge from the clinic, the research nurse will review the following information with the patient:

- The toxicities of each agent and how to treat/prevent them
- The signs and symptoms to report to the study team
- How to complete the medication self administration record (patient diary)(See Appendix F for lapatinib-specific medication diary).
- Instructions to carefully observe for signs and symptoms of AEs
- Potential risks regarding pregnancy and fetal exposure
- Study agents should never be shared

Patients will be dispensed 1 cycle of drug at a time (Section 5.3.7). At each cycle prior to drug dispensing, the toxicity information as described in section 7 will be reviewed with the patient.

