## 5.2 Dosing Delays/Modifications

General guidelines for treatment modifications at the time of re-treatment:

Adverse Events: All adverse events in this trial will be graded using the NCI Common Terminology Criteria for Adverse Events (CTCAE) version 4.0 - a complete listing is available at the CTEP website:  
<http://ctep.cancer.gov/forms/CTCAEv4.pdf>.

Dose adjustments will be made according to the guidelines below, with dose levels defined as follows:

Dose Level (DL)	Agent Dose
0	Lapatinib 500 mg twice daily
-1*	Lapatinib 1000 mg once daily

-2*	Lapatinib 750 mg once daily
-----	-----------------------------

\* The Cmax for lapatinib is higher when administered at a BID dose.

Please refer to Table 2 (background section) for specific values.

**Table 5** Summary of dose holding/interruptions and dose de-escalation recommendations for lapatinib in case of lapatinib-related adverse events (graded according to NCI-CTCAE v4.0)

General Adverse Events	Action
Non-hematological, Grade 1 or 2	Continue lapatinib therapy at full dose prescribed. Apply maximum supportive care recommendations. If prolonged duration of Grade 2 adverse event ( $\geq 7$ days) is affecting quality of life, decrease dose to DL -1, if symptoms persist and continue to affect quality of life for $\geq 7$ more days, a second dose reduction to DL -2 will be allowed.
Non-hematological, Grade 3 or 4 (excluding cardiac and hepatobiliary events)	Apply maximum supportive care recommendations. Hold lapatinib therapy until recovery to Grade $\leq 1$ (up to 14 days). For NCI-CTCAE v4.0 Grade 3 or 4 interstitial pneumonitis or Grade 4 rash manifested as toxic epidermal necrolysis (e.g. Stevens-Johnson Syndrome etc) lapatinib must be permanently discontinued If recurrence of adverse event after drug hold/interruptions is observed, and maximum supportive care measures applied, hold drug once again until recovery to Grade $\leq 1$ (up to 14 days) and restart drug at DL-1. If adverse event recurs, a second dose reduction to DL -2 will be allowed after symptoms recover to Grade $\leq 1$ .
Non-hematological, Grade 3 or 4 adverse events NOT resolved to Grade $\leq 1$ within a maximum of 2 weeks from last planned administration	Action (discontinue or resume lapatinib therapy) in individual cases after discussions with the Sponsor. Up to 2 reductions (DL-1 and DL-2) will be considered after maximum supportive care recommendations are introduced.
Cardiac Adverse Events	

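### Two pulmonary dosing rules appear only in the expedited-reporting section (7.3.5) and are missing from Table 5, where sites are sent for dose modifications

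*Combined protocol and SAP*

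**What the plan says.** Section 5.1 places adverse events and risks in Section 7 and says that dose modifications "are described in Section 5.2 below".

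Section 5.2 opens with "General guidelines for treatment modifications at the time of re-treatment". Its Table 5 is titled "Summary of dose holding/interruptions and dose de-escalation recommendations for lapatinib in case of lapatinib-related adverse events". The parts that bear on pulmonary events are:

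- **Non-hematological Grade 1-2 row:** "Continue lapatinib therapy at full dose prescribed". The only departure is a dose reduction for prolonged Grade 2 events that affect quality of life. No organ system is excluded.
- **Non-hematological Grade 3-4 row**, "excluding cardiac and hepatobiliary events": hold until Grade 1 or less, for up to 14 days. If the event recurs, hold again and restart at a lower dose level. The row also has one pulmonary instruction: "For NCI-CTCAE v4.0 Grade 3 or 4 interstitial pneumonitis", lapatinib is stopped for good.
- **Row for Grade 3-4 events unresolved at 2 weeks:** discontinue or resume case by case, after discussion with the Sponsor.

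Section 7.3.5 sits under a heading about expedited reporting. Its Pulmonary Events paragraph contains:

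- "If a patient develops symptoms suggestive of interstitial pneumonitis, adult respiratory distress syndrome (ARDS), or non-cardiogenic pulmonary edema, lapatinib therapy should be interrupted", followed by a thorough evaluation.
- A permanent stop if Grade 3-4 pneumonitis or pulmonary fibrosis is confirmed and a link to lapatinib cannot be excluded.
- Reporting of all interstitial lung disease or pneumonitis as an SAE, whatever the grade.

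**The concern.** A site deciding whether a patient should keep taking lapatinib is directed to Section 5.2. For two pulmonary situations the stricter rule is not there. Because Table 5 does name Grade 3-4 interstitial pneumonitis, a reader could reasonably take it as the whole pulmonary rule.

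Where the two texts differ, the section that sites are sent to for dosing gives the less safe instruction. Section 7.1 lists pneumonitis among the rare but serious events. At stake are a patient's continued exposure during early pneumonitis, or re-exposure after severe fibrosis, and uneven handling across the participating sites.

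**Working it through.** The plan states no figure on this point. The check is a comparison of the two texts, followed by a ceiling on the number of patients.

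**Side by side**

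| Situation | Table 5 (Section 5.2) | Section 7.3.5 | Agreement |
|---|---|---|---|
| Suggestive symptoms, not yet graded or attributed | No rule (the table covers lapatinib-related events) | Interrupt and evaluate | Table 5 silent |
| Related, symptomatic Grade 1-2 pneumonitis | Continue full dose | Interrupt and evaluate | Literal conflict |
| Grade 1-2 pneumonitis without symptoms | Continue full dose | Interruption not triggered | No clear conflict |
| Grade 3-4 interstitial pneumonitis | Permanent stop | Permanent stop if confirmed and a link cannot be excluded | Consistent on the stop |
| Confirmed Grade 3-4 pulmonary fibrosis, link not excluded | Hold; restart possible after recovery or Sponsor discussion | Permanent stop | Conflict |
| Confirmed Grade 3-4 ARDS or non-cardiogenic pulmonary edema | Hold; restart possible | Interrupt and evaluate; no mandatory stop | Compatible |

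**Cross-references.** Cardiac events have a Table 5 row that points to Section 5.2.1, and the cardiac paragraph of 7.3.5 points there too. Pulmonary events have no such link in either direction.

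**Ceiling on numbers.** Inputs:

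- Rate p below 0.03. This is the column heading in Section 7.1 under which pneumonitis is listed, and the only rate in the documents.
- n = 16, the first stage (Section 12.1).
- n = 28, the treatment ceiling including up to 3 inevaluable patients (Section 12.2).

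Expected any-grade cases = n × p:

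- 16 × 0.03 = 0.48, so fewer than 0.48.
- 28 × 0.03 = 0.84, so fewer than 0.84.

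Only the related, symptomatic Grade 1-2 cases among these meet the literal conflict. The documents do not give that share. Pulmonary fibrosis is in neither adverse-event list of Section 7.1, so no rate can be attached to it.

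**What assumptions would add.** Assume an any-grade rate of 0.5% to 2%, with 25% to 75% of cases related, symptomatic and Grade 1-2.

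- The conflict rate q runs from 0.005 × 0.25 = 0.00125 to 0.02 × 0.75 = 0.015.
- The chance of at least one such case, 1 − (1 − q)^n, runs from 2% to 21% for n = 16 and from 3% to 35% for n = 28.

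The width comes entirely from the assumed inputs, so the conclusion does not use these figures.

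**The case against.** The strongest reply is that the specific rule governs the general one. Table 5 already works that way. Its Grade 1-2 row, read literally, would also keep full dose for Grade 2 AST/ALT or Grade 1 bilirubin elevation, yet the hepatobiliary rows hold lapatinib for 2 weeks. The general row yields there without any stated priority. Section 5.2 also calls its content general guidelines, while 7.3.5 makes its stop mandatory. This narrows the conflict but does not remove it. The hepatobiliary rows sit in the same table, in view of the reader. The pulmonary rule sits in a reporting section with no link.

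Second, the two texts act at different moments. Section 7.3.5 acts on suspicion, whereas Table 5 acts on a graded, related event. A site can interrupt, evaluate, and then apply Table 5. That works only if the site has read 7.3.5 before deciding on dose.

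Third, there are safeguards:

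- Section 5.1 adds that "At each cycle prior to drug dispensing, the toxicity information as described in section 7 will be reviewed with the patient".
- A physician or designee decides on continuation before dispensing (Section 5.3.7).
- Unacceptable adverse events end treatment (Section 5.8).
- Every interstitial pneumonitis is an SAE under the same paragraph that holds the dosing rules, and the principal investigator reviews all SAEs (Section 6.3).

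These make harm less likely. None says which dosing rule applies, and SAE reporting follows the event.

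Fourth, the fibrosis gap is thin. Table 5 already holds lapatinib at Grade 3-4, and resumption needs recovery or Sponsor discussion. That stands. What is missing is the mandatory stop.

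**Conclusion.** The point holds as an inconsistency in dosing instructions. Two pulmonary rules are absent from the section that sites are told to use, and for two situations a literal reading of that section gives a less safe instruction. Few if any patients would be affected: fewer than 0.48 expected pneumonitis cases of any grade in 16 patients and fewer than 0.84 in 28, with only some of them in the conflict. This takes the under-3% heading as a ceiling that applies to this population. The fibrosis case is remote.

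A reader might infer more than the documents support:

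- **That Table 5 would keep treating severe pneumonitis.** It stops lapatinib for Grade 3-4 interstitial pneumonitis.
- **That 7.3.5 orders interruption for pneumonitis of every grade.** The words about all grades attach to SAE reporting. The interruption rule has no grade threshold but is triggered by symptoms.
- **That Grade 1-2 ARDS or pulmonary edema would continue at full dose.** Whether those events can be Grade 1-2 depends on the CTCAE scale, which the documents do not reproduce.
- **That the trial's conclusions are at risk.** The two-stage rule, its error rates and the response endpoint are unchanged.

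It should be corrected because the event class is serious and the correction is nearly free.

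**What to change.** In an amendment:

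1. Add a pulmonary row to Table 5 using the 7.3.5 wording. It would require interruption and evaluation on symptoms pointing to interstitial pneumonitis, ARDS or non-cardiogenic pulmonary edema, and a permanent stop for confirmed Grade 3-4 pneumonitis or pulmonary fibrosis when a link to lapatinib cannot be excluded.
2. State that this row takes precedence over the general non-hematological rows in two circumstances only: while suggestive symptoms are being evaluated, and for confirmed Grade 3-4 pneumonitis or pulmonary fibrosis.
3. Cross-reference Table 5 and 7.3.5 to each other.

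Keep confirmed Grade 3-4 ARDS and non-cardiogenic pulmonary edema under the existing Grade 3-4 hold row. Excluding every pulmonary event from the general rows would take these two out of the only row that gives them a hold and restart rule, because 7.3.5 mandates a stop only for pneumonitis and fibrosis. Leave resumption after confirmed Grade 1-2 pneumonitis to the sponsor's clinical judgment.

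The cost is one table row, one sentence on precedence and two cross-references. No clinical rule or procedure is added, since 7.3.5 already requires the interruption, the evaluation and the stop.
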